Study Protocol: Effectiveness of Bilateral PTNS compared to Unilateral PTNS for the Treatment of Overactive Bladder/Urge IncoNtinence (BUTTON)

Clinical trials: NCT 03535857

Protocol Date: 4/30/2024

Scientific Background

Overactive bladder (OAB) is defined as a syndrome of urinary urgency, usually associated with frequency with or without incontinence (1). This syndrome is estimated to affect more than 16 % of the adult population (2) and has a significant impact on the quality of life of those affected by it (3). The treatment algorithm as recommended by the American Urologic Association includes starting with behavioral modifications then offering pharmacologic therapy if needed (4). Previous data show that adherence to pharmacologic therapy is low due to side effects and thus there is a high discontinuation rate (5). One of the approved treatments with a low side effect profile is percutaneous posterior tibial nerve stimulation (PTNS) (4).

The SUmiT trial, a randomized controlled study for OAB has shown that when compared to sham, PTNS demonstrated 54% improvement in symptoms subjectively as compared to 20% in the sham arm. In addition, PTNS was associated with a better reduction of incontinence episodes and daily number of voids (6).

The OrBIT study which randomized women with OAB to PTNS or extended release tolterodine found a larger number of women receiving PTNS (79.5% vs. 60 %) who reported significant improvement in symptoms (7).

PTNS device has been cleared by FDA for the treatment of overactive bladder and urge urinary incontinence. It however does not state whether stimulation of the posterior tibial nerve should be performed unilaterally or bilaterally. The above studies using PTNS have all involved unilateral percutaneous stimulation of the posterior tibial nerve. We do not yet know whether bilateral stimulation produces a different result from the traditional unilateral stimulation.

A study of sacral neuromodulation, also an approved second tier OAB treatment which stimulates the sacral nerve demonstrated that 76% of patients with bilateral lead implants had more than 50% improvement in overactive bladder symptoms as compared to 58% of those who had unilateral lead placement (8). A percutaneous nerve evaluation pilot study for those who failed sacral neuromodulation revealed that a select group of patients benefited from bilateral stimulation (9). There have been no bilateral PTNS studies for OAB to date. Though the colorectal literature suggests bilateral transcutaneous stimulation of the posterior tibial nerve improves fecal incontinence (10). The aim of our study is to compare the effectiveness of bilateral tibial nerve stimulation versus unilateral tibial nerve stimulation in managing overactive bladder symptoms using PTNS device. The study will not be evaluating the effectiveness of the device itself but rather comparing stimulation of one nerve versus two nerves using a device that is already on the market.

Study Objectives

Percutaneous tibial nerve stimulation (PTNS) is an accepted treatment for overactive bladder that can be accomplished in the office with minimal side effects. It is currently carried out by stimulating one of the posterior tibial nerve unilaterally.

The aim of this study is to determine whether bilateral percutaneous tibial nerve stimulation is more effective than unilateral stimulation.

Patients with a diagnosis of overactive bladder or urge incontinence who have previously failed lifestyle changes and/or pharmacologic therapy will be offered percutaneous tibial nerve stimulation. Enrolled patients will be randomized into two groups. The control group will receive the traditional unilateral treatment of PTNS. The intervention group will receive bilateral PTNS treatment during the study period. Intervention success will be measured by an improvement in the scores on the overactive bladder questionnaire and incontinence impact questionnaire as well as a decrease in the number of daily voids, nocturia episodes as assessed by voiding diaries.

Hypothesis

Bilateral PTNS is more effective than unilateral PTNS at reducing symptoms of OAB.

Primary Aim: Compare improvement of overactive bladder symptoms of participants receiving bilateral PTNS to those receiving unilateral PTNS using the overactive bladder questionnaire (OAB-q).

Secondary Aim(s):

- 1. Evaluate impact of OAB on quality of life using the incontinence impact questionnaire
- 2. Compare the number of voids per 24-hour periods
- 3. Compare the number of nighttime voids
- 4. Compare the number of incontinence episodes

Study Design and Methods:

This will be a randomized study of patients with overactive bladder not naive to behavioral therapy and/or pharmacotherapy (or unable to tolerate or with contraindications to pharmacotherapy) with or without urge incontinence recruited through the outpatient offices of the Division of Urogynecology at Women and Infants Hospital and University of Pittsburgh Medical Center Magee-Womens Hospital. The patients will be randomized to receiving unilateral or bilateral PTNS for 30 minutes weekly for a total of 12 weeks. Though we considered the use of a sham needle to decrease participants' bias in reporting their results, we have elected not to use a sham needle. Since all participants will be naïve to PTNS, they are unable to gauge the amount of improvement they should have and therefore we can expect reported improvement to be accurate.

Participants will be asked to complete a 2-day bladder diary at baseline and weekly as per routine PTNS care. Participants will also be asked to fill out a validated OAB symptom severity questionnaire (OAB-q) and the incontinence impact questionnaire (IIQ-7) at baseline (+/- 1 week), four weeks (+/- 1 week), eight weeks (+/- 1 week) and twelve weeks (+/- 1 week).

Our primary outcome will be the improvement in symptom severity as measured by the OAB-q score.

Secondary outcomes will include change in the number of daily voids, change in nocturia or night time voids, change in number of incontinence episodes as measured by the bladder diary and, impact in quality of life as demonstrated by change in score of the incontinence impact questionnaire, IIQ-7.

All questionnaires collected from participants will be labeled with a unique study number and any participant identifiers on the questionnaires or voiding diary will be redacted prior to saving in a research folder in a locked drawer.

Inclusion criteria

Female patients over the age of 18 who have previously tried and failed, or were unable to tolerate, behavioral therapy. Patients will have to consent to participate in the study. Patients on pharmacologic therapy at the time of recruitment will continue their treatment.

Exclusion criteria

- 1. Pregnant patients
- 2. Patients with pacemakers of implantable defibrillators
- 3. Patients with neurogenic bladder
- 4. Patients who have received Botox or have an implant for sacral nerve stimulation
- 5. Patients with uncontrolled bleeding disorder
- 6. Patients with unhealed ulcers or with leg edema surrounding medial malleolus

Rationale for exclusion criteria

PTNS is an approved procedure that was not previously studied in the pregnant population therefore we will exclude pregnant patients from this study. PTNS is the electrical stimulation of the tibial nerve through a needle and therefore it is unclear how this stimulation would interact with a pacemaker or implantable defibrillator.

While patients with neurogenic bladder may have overactive bladder, the pathophysiology of their urinary frequency and incontinence is different therefore including them in this particular study has the potential to confuse the study results. Botox and Interstim (implantable sacral nerve stimulator) are advanced overactive bladder therapies and are generally offered to those who have failed pharmacotherapy and PTNS and therefore PTNS is unlikely to be effective in participants that have failed more advanced therapies. A needle is inserted through the skin for PTNS and thus PTNS conjures a potential for bleeding. Therefore, those with bleeding disorders will be excluded. Electrical stimulation is sent to the tibial nerve through a needle and therefore leg ulcers and edema can potentially alter the stimulation received by the nerve.

Sample Size calculations

Based on the SUmiT trial results, we expect a decrease in OAB symptom severity of 36.7 with a standard deviation of 21.5 in the unilateral PTNS group. If we estimate that the bilateral PTNS group will show at least 50 % improvement from the unilateral, then we should see an average decrease in in symptom severity of 55 in the bilateral PTNS group.

Our sample size estimate based on 5% significance and 80 % power with a standard deviation of 21.5 will be: 23 per group for a total of 46 participants.

If we expect an attrition rate of about 10%, our goal is therefore to recruit a total of 50 participants with 25 participants in each arm.

Statistical Analysis

Descriptive statistics will be used to assess the balance of baseline characteristics between randomization groups: unilateral and bilateral PTNS groups. The primary analysis will be intent-to-treat. At baseline, for both treatment groups, the Wilcoxon-rank sum test will be used for all continuous variables and Fisher's exact test for all categorical variables. For the analysis of primary and secondary outcomes, we will compare the last measurement to the baseline measurement within and between treatment groups in OABq score, IIQ-7, daily number of voids, number of nighttime voids, and number of incontinence episodes between the unilateral and bilateral PTNS groups using a pairwise t-test (using a Bonferroni adjustment). These comparisons will result in three sub-analyses: the changes of the primary and secondary outcomes within the unilateral PTNS group, within the bilateral PTNS group, and between the groups (taking the differences between the baseline and last measurement between the groups).

Recruitment and enrollment

Patients with overactive bladder or urge urinary incontinence who have failed behavioral or pharmacologic therapy will have all advanced therapy options presented to them as part of their clinical care by their physician. Those who choose to have PTNS will be approached about the study either by the physician or the research coordinator. If the patient meets eligibility and wishes to participate, they will be consented. In addition, patients who present for their first PTNS visit but were not previously approached about this study will be asked about participating in the study and consented if they are willing

Randomization

Randomization has been performed by a member of the staff at Women and Infants Hospital not part of the research team. Randomization has been concealed in opaque envelopes. Assignment of the randomization envelope to each subject will occur after the patient has signed consent.

Intervention

There will be 12 weekly PTNS treatments of 30 minutes. At the first visit, the participant will complete the OAB questionnaire and the incontinence impact questionnaire. This will be repeated at weeks 4, 8 and 12.

Participants will also be asked to fill out a weekly 2-day bladder diary as is routinely done for PTNS which they will bring to their visit. The bladder diaries will be provided to the participants at the initial visit. Participants will be instructed to fill out the bladder diary for 48 hours including all fluid intake, voids and any leakage.

Participants who are randomized to unilateral PTNS stimulation will have one ankle stimulated for 30 minutes weekly for a total of 12 sessions. Participants who are randomized to bilateral stimulation will have both ankles stimulated simultaneously for 30 minutes weekly for a total of 12 sessions.

PTNS stimulation is performed with a fine needle electrode that is inserted just below the skin in the medial ankle. This needle electrode is connected to a handheld stimulator through a lead wire. The handheld stimulator is then used to administer electrical impulses to the needle electrode increasing the current to a level that leads to a motor response and is comfortable to the participant.

References

1. Haylen BT, de Ridder D, Freeman RM et al: An International Urogynecological Association (IUGA)/International Continence Society (ICS) joint report on the terminology for female pelvic floor dysfunction. Neurourol Urodyn 2010; 29 (1): 4-20.

2. Stewart WF, van Rooyen JB, Cundiff GW et al. Prevalence and burden of overactive bladder in the United States. World j Urol 2003; 20: 327-336

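### Does the statement that PTNS-naive participants will report accurately, in an unmasked trial with only self-reported outcomes, call for a change to the plan?

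*Combined protocol and SAP*

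**What the plan says.** Study Design and Methods raises the issue itself. It says a sham was considered because of participants' "bias in reporting their results, we have elected not to use a sham needle". One reason follows. Its premise is that every woman enrolled will be new to the treatment, and from this the section concludes that "they are unable to gauge the amount of improvement they should have and therefore we can expect reported improvement to be accurate".

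The same section sets the endpoint: "Our primary outcome will be the improvement in symptom severity as measured by the OAB-q score". The secondary outcomes are the IIQ-7 and, from the bladder diary, daily voids, night-time voids and incontinence episodes.

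The Intervention section describes what each woman experiences. In the unilateral arm she "will have one ankle stimulated for 30 minutes weekly for a total of 12 sessions"; in the bilateral arm she "will have both ankles stimulated simultaneously for 30 minutes weekly for a total of 12 sessions". The current is raised until there is a motor response. The Randomization section describes opaque envelopes opened after consent. No masking after assignment is described.

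At the end of Scientific Background the study is described as not evaluating the device, but "rather comparing stimulation of one nerve versus two nerves using a device that is already on the market".

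**The concern.** The protocol names a bias and then sets it aside with a reason that does not answer it. A between-arm comparison is biased when expectations differ by arm. Having no previous PTNS to compare with does not prevent that. Each woman can see and feel whether one or both ankles are stimulated at each of the 12 sessions, and the trial's own hypothesis is that bilateral treatment works better. Every listed outcome is recorded by the participant, so none offers an independent check. Scientific Background also cites 20% subjective improvement in the sham arm of an earlier PTNS trial, which shows that improvement can be reported without active stimulation.

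At stake is the interpretation of a positive result. If it were read as the physiological effect of a second nerve, it would claim more than an unmasked self-report comparison can show. A further worry is that the criteria list does not mention previous PTNS, so the naivety on which the argument rests is stated rather than secured by eligibility.

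**Working it through.** **1. Does the inference hold?** Set the sections side by side.

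- Study Design and Methods: naive women cannot judge how much improvement to expect. This concerns a benchmark. The text does not say that naivety conceals the arm.
- Intervention: one ankle against both, with current raised to a motor response. The arm is evident to the participant.
- Study Design and Methods and Intervention: both questionnaires and the diary are completed by the participant.

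Naivety may remove comparison with past PTNS, but not awareness of the arm. The claim of accuracy therefore does not follow from the reason given.

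**2. The plan's own figure.** Sample Size calculations states "we expect a decrease in OAB symptom severity of 36.7 with a standard deviation of 21.5 in the unilateral PTNS group" and a decrease of 55 in the bilateral group.

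- Planned difference: 55 − 36.7 = 18.3 points.
- Normal approximation: n per arm = 2 × (1.960 + 0.842)² × 21.5² / 18.3² = 21.7, so 22.
- Two-sided t-test at 5% with 80% power: 22.67, so 23 per arm, as stated. Power at 23 per arm is 80.6%.

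The stated sample size reproduces, and nothing in this concern alters it.

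**3. What an expectation shift could do (illustration only).** The documents give no size for such a shift, so the values below are assumptions; 9.15 is simply half of 18.3. Take no true difference, 23 per arm, SD 21.5 and a shift of b points in favour of bilateral treatment.

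- SE = 21.5 × √(2/23) = 6.34, with df = 44.
- Smallest observed difference significant at unadjusted 5%: about 12.8 points.
- Chance of significance: two-sided noncentral t with noncentrality b / 6.34.

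| Shift b | Share of 18.3 | α = 0.05 | 0.05/3 | 0.05/5 | 0.05/15 |
|---|---|---|---|---|---|
| 0 | 0% | 5.0% | 1.7% | 1.0% | 0.33% |
| 3 | 16% | 7.5% | 2.9% | 1.8% | 0.7% |
| 5 | 27% | 12.0% | 5.2% | 3.5% | 1.5% |
| 7.5 | 41% | 21.2% | 10.6% | 7.6% | 3.5% |
| 9.15 | 50% | 29.2% | 15.9% | 11.8% | 5.9% |

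Statistical Analysis specifies a Bonferroni adjustment without giving the number of comparisons, so the divisors 3, 5 and 15 are also assumptions. The table shows only that a larger assumed bias gives more false positives. It is not evidence that a bias of any given size exists. Whatever its size, a shift enters the estimated difference in full, and neither a Bonferroni adjustment nor a larger sample removes it.

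**4. What would a change achieve?** The available edit replaces the accuracy sentence with a statement that participants are unmasked and that the difference includes any expectation effect. Conduct, outcomes, randomization, sample size and analysis all stay the same. The estimate and its bias are identical before and after the edit.

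**5. The related points.**

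- The one-nerve-versus-two sentence in Scientific Background separates this trial from a test of the device. It describes the two arms and does not claim that any difference excludes expectation.
- The documents contain no text for the trial's conclusions, so there is no overstated conclusion to correct.
- On previous PTNS, Recruitment and enrollment describes women who choose PTNS or who attend a first PTNS visit. That agrees with the stated naivety, and nothing shows previously treated women entering. An exclusion line would only write down a premise already applied.

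**The case for a change.** The strongest case for a change is that the protocol does more than leave its participants unmasked, which is common and acceptable. It asserts that reports will be accurate, on a reason that fails, and this is its only answer to a bias it names itself. One sentence would correct it at almost no cost and at any stage of the trial. An unknown direction of bias is no support for a claim of accuracy. Diary counts may be less prone to bias than questionnaire scores, but they too are self-recorded, and the primary outcome is a questionnaire.

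Most of this stands as criticism of the sentence: the inference is weak and the wording too confident. It does not stand as a case for amending the plan. The trade-off is disclosed, with the bias, the sham option and the decision all on the page. A statistician reading the Intervention section will see that participants know their arm and will treat the comparison as open-label. A differential expectation effect is plausible, but the documents do not show what women are told about the likely benefit of each arm.

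**Conclusion.** The concern is right about the sentence and does not lead to a change in the plan. PTNS-naivety does not make unmasked self-report accurate, and the difference between arms may include an expectation effect of visibly bilateral treatment. That effect comes with an open comparison using participant-reported outcomes, which the protocol chose knowingly. Rewording the rationale would not separate stimulation from expectation, and no stated figure, analysis or procedure would differ. The planned 23 per group reproduces.

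The size of any bias cannot be derived from the documents. The range of 7.5% to 29.2% rests on assumed shifts of 3 to 9.15 points, no true difference and no multiplicity adjustment. For the 9.15-point shift the adjusted values are 15.9%, 11.8% or 5.9%, depending on an assumed number of comparisons. These figures describe sensitivity and should carry no weight beyond that. The trial estimates bilateral against unilateral PTNS as delivered to women who know their arm, and the report of results is the natural place to say so.

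### The primary analysis is an unadjusted t-test of change to the last measurement; a baseline-adjusted week-12 analysis of scores already scheduled would be more precise and would fix the time point

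*Combined protocol and SAP*

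**What the plan says.** The protocol and SAP are one document. Under Statistical Analysis, "The primary analysis will be intent-to-treat". For the OAB-q, the IIQ-7 and the three diary outcomes, "we will compare the last measurement to the baseline measurement within and between treatment groups". The between-arm comparison is made by "taking the differences between the baseline and last measurement between the groups", and the test is a t-test with a Bonferroni adjustment for an unstated number of comparisons. No baseline covariate is named, and nothing is said about scores that are missing.

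Study Design and Methods schedules the two questionnaires "at baseline (+/- 1 week), four weeks (+/- 1 week), eight weeks (+/- 1 week) and twelve weeks (+/- 1 week"). Under Intervention they are completed at the first visit, and "This will be repeated at weeks 4, 8 and 12". Diaries are more frequent: "Participants will be asked to complete a 2-day bladder diary at baseline and weekly as per routine PTNS care". The primary outcome is defined as improvement in OAB-q symptom severity, without a time point. Sample Size calculations expects about 10% attrition and uses that figure only to raise recruitment from 46 to 50.

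**The concern.** Two features of this analysis can be improved with data the trial already collects.

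- **Precision.** A t-test on raw change fixes the weight given to the baseline score instead of estimating it. In a trial of about 45 to 50 people sized at 80% power, that can discard useful information. The week-4 and week-8 scores are also unused, except as possible stand-ins.
- **The early leavers.** Taken literally with intent-to-treat, the last measurement for someone who leaves is a week-4 or week-8 score, taken before the 12 sessions are complete. That measures outcome at departure, not the difference after the full course. If only week-12 scores count, these participants drop out of an analysis that is called intent-to-treat. The text does not say which is meant, so the choice could be made after the data are seen. For the weekly diaries, the last record of an early leaver could come from any week.

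**Working it through.** **Inputs from Sample Size calculations:** mean decrease 36.7 (unilateral) and 55 (bilateral), so difference 18.3; SD 21.5; 5% significance; 80% power; 23 per group; about 10% attrition; 25 recruited per arm.

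**Assumptions not in the documents:** the test is two-sided; 21.5 is the SD of change; ρ is the correlation of baseline with week 12; k is the ratio of week-12 SD to baseline SD; f is the share of the week-12 effect present at departure. Bonferroni is left out throughout.

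**1. The plan's own figure.** The normal approximation gives n = 2(1.96 + 0.8416)² × 21.5² / 18.3² = 21.7, so 22 per arm. The t-based solution is 22.67, so 23 per arm, as stated.

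**2. The planned test.** After 10% loss, 50 × 0.9 = 45, or 22.5 per arm. The t-test on change has power 0.797. With no loss (25 per arm) it is 0.839.

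**3. Baseline adjustment.** The residual variance relative to the variance of change is k²(1 − ρ²) / (1 + k² − 2ρk), which reduces to (1 + ρ)/2 when k = 1. Power at 22.5 per arm:

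| k | ρ = 0.3 | ρ = 0.5 | ρ = 0.7 |
|---|---|---|---|
| 0.8 | 0.976 | 0.958 | 0.941 |
| 1.0 | 0.933 | 0.897 | 0.857 |
| 1.3 | 0.875 | 0.832 | 0.801 |
| 1.5 | 0.848 | 0.811 | 0.798 |

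For k = 1 the residual SDs are 17.3, 18.6 and 19.8. A simulation of week-12 ANCOVA with 10% random loss (60,000 runs each, k = 1) gave 0.925, 0.888 and 0.845 to 0.848, about one point lower than the formula.

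If 21.5 is instead the SD of the score (k = 1), the unadjusted test has power 0.655, 0.797 and 0.950 at the three correlations, against 0.833, 0.897 and 0.974 adjusted.

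**4. What the week-4 and week-8 scores add.** Without baseline adjustment, let r be the correlation between the earlier scores and week 12. The effective n per arm is 1 / ((1 − r²)/22.5 + r²/25). For r = 0.4, 0.6 and 0.8, power is 0.804, 0.812 and 0.824, against 0.797 for completers. The gain is at most 2 to 3 points.

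**5. Carry-forward with equal loss.** With proportion p lost and full effect D, the arm mean is D(1 − p(1 − f)) and the variance is 21.5² + p(1 − p)(D(1 − f))². With p = 0.10 in both arms, the difference is 18.3 × (1 − 0.1(1 − f)). Power is at 25 per arm.

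| f | Difference | Power |
|---|---|---|
| 1/3 (linear, leaves after week 4) | 17.08 | 0.714 |
| 2/3 (linear, leaves after week 8) | 17.69 | 0.795 |
| 0.70 | 17.75 | 0.801 |
| 0.85 | 18.03 | 0.824 |
| 0.90 | 18.12 | 0.830 |

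**6. Carry-forward with unequal loss.** The shift in the difference is −(1 − f)(55·p_b − 36.7·p_u), where p_b and p_u are the losses in the bilateral and unilateral arms.

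- At 12% bilateral and 8% unilateral: 6.60 − 2.94 = 3.66. The difference is 18.3 − 2.44 = 15.86 at f = 1/3, and 17.08 at f = 2/3.
- At 8% and 12%: 4.40 − 4.40 = 0, so the difference stays at 18.3.
- It rises above 18.3 only when unilateral loss exceeds 55/36.7 = 1.5 times bilateral loss.
- With no true difference (36.7 in both arms), a 12%/8% split at f = 1/3 shifts the result by 36.7 × 0.04 × 2/3 = 0.98 points against the arm with more loss.

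**The case against.** A reader might infer that the plan has no week-12 assessment. It does. Both questionnaires are scheduled to week 12 with a window, and for anyone who completes the course the last OAB-q is the week-12 score. What is unsettled for the primary outcome concerns about 5 of 50 people. Raising recruitment to cover attrition also suggests that those lost were not expected to be analysed. That makes the week-12 reading more natural than carry-forward, although it conflicts with intent-to-treat.

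A reader might also infer that the planned test is wrong or underpowered. The documents do not support this. A t-test on change is valid under randomisation, matches the basis of the sample size and, among completers with random loss, has the planned power. It is less efficient, not incorrect.

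A third tempting reading is that carry-forward seriously biases the result. At equal 10% loss it does not. The lowest power in the table, 0.714, requires every leaver to stop after week 4 with linear build-up. Severe imbalance between arms has no source in the documents. Power lost to the Bonferroni adjustment is a separate matter and adds no weight here.

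Finally, the gain from adjustment depends on a correlation and a variance ratio that the documents do not give. This stands: the gain can be near zero, as the lower rows of the first table show. Any loss, of about one degree of freedom, is negligible.

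**Conclusion.** The point holds as an improvement to the choice of analysis, not as an error that invalidates the trial. Over the range k = 0.8 to 1.3 and ρ = 0.3 to 0.7, baseline adjustment moves power from 0.80 to between 0.80 and 0.98; with equal variances the range is 0.86 to 0.93. Most of the benefit comes from the baseline covariate and applies to every participant. The repeated measures mainly provide a principled way to keep the early leavers in the analysis.

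Carry-forward is the smaller issue: 18.3 falls to about 17.1 to 18.1 with equal 10% loss. Unequal loss can move the estimate either way. Outcome at departure is a legitimate target if the sponsor wants it, but the plan would have to say so. These sizes rest on the assumptions listed with the calculation.

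**What to change.** - Define the primary estimate as the between-arm difference in OAB-q symptom severity at week 12 (+/- 1 week) in all randomised participants.
- Estimate it from a baseline-adjusted repeated-measures model using the scheduled week 4, 8 and 12 scores. A week-12 ANCOVA with multiple imputation from the earlier scores is an acceptable alternative.
- State how a participant with only a baseline score is handled.
- Name week 12 as the time point for the IIQ-7 and the diary outcomes.
- Keep the change to last measurement as a sensitivity analysis.

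The cost is revised wording and slightly more analysis work in standard software. It needs no extra visits or participants. The main model relies on scores being missing at random. The last-measurement analysis makes a different assumption about those who leave, so comparing the two shows how much the result depends on it.

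### The between-arm t-test on raw change in the 2-day diary counts ignores the baseline count; it is valid but inefficient, and for incontinence episodes a few heavy leakers may dominate it

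*Combined protocol and SAP*

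**What the plan says.** The Statistical Analysis section handles all five outcomes alike. For the diary outcomes it compares "daily number of voids, number of nighttime voids, and number of incontinence episodes between the unilateral and bilateral PTNS groups using a pairwise t-test", with a Bonferroni adjustment. The between-group contrast is the difference between baseline and last measurement, compared across arms. No baseline covariate, transformation, count model or rank test is planned for any outcome. Rank methods appear only for baseline characteristics, where "the Wilcoxon-rank sum test will be used for all continuous variables and Fisher's exact test for all categorical variables".

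The counts come from a short diary. Under Intervention, women are told to "fill out the bladder diary for 48 hours including all fluid intake, voids and any leakage". Under Study Design and Methods, women may enrol whether or not they leak, so some may have no leaks at baseline. Three of the four secondary aims are diary counts.

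The sample size rests on OAB-q symptom severity alone: "5% significance and 80 % power with a standard deviation of 21.5 will be: 23 per group for a total of 46 participants". The documents give no mean, SD, distribution or power for any diary count.

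**The concern.** A woman with 20 leaks in 48 hours can fall by far more than a woman with 2. If treatment acts roughly in proportion, raw change largely restates how much each woman leaked at the start. That between-woman spread goes into the error term of a t-test on change, although the baseline count that would explain much of it has been recorded. If leak counts are strongly skewed, a few women supply most of the variance.

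At stake is what a null diary result would mean. If the planned test would usually miss a true further halving of leaks, a non-significant result could be misread as no added benefit from bilateral stimulation.

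**Working it through.** **1. The plan's own figure.** Inputs from Sample Size calculations: decreases of 36.7 and 55, SD 21.5, 5% significance, 80% power. Sidedness is not stated; two-sided is assumed.

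- Difference: 55 - 36.7 = 18.3. Standardised: 18.3 / 21.5 = 0.85.
- Normal approximation: n = 2 × (1.96 + 0.84)² / 0.85², about 22 per arm. The two-sample t calculation gives 22.67, so 23, with power 80.6%. One-sided would give 18. The stated 23 reproduces.
- After 10% attrition, 25 × 0.9 = 22.5, so about 23 per arm are analysed.
- With 23 per arm, a t-test has 80% power only for a difference of 0.84 SD at 5%, or 1.05 SD at 1% (Bonferroni over five outcomes, an assumption because the number of tests is not stated).

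**2. Why raw change is noisy.** Assume leaks fall by 40% in the unilateral arm and bilateral treatment halves them again. The follow-up multipliers are 0.6 and 0.6 × 0.5 = 0.3.

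- At a rate of 2 leaks, the expected change is -0.8 (unilateral) or -1.4 (bilateral).
- At the assumed mean of 6, it is -2.4 or -4.2, an arm difference of 1.8.
- At a rate of 20, it is -8 or -14.

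Within the unilateral arm, expected change runs from -0.8 to -8 between the lighter and the heavier leaker. That spread of 7.2 is four times the arm difference at the mean.

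**3. Leaks, simulated.** All distributional inputs are assumptions: 23 per arm, baseline Poisson with gamma rates (mean 6 per 48 hours, shape k), the multipliers above, lognormal variation in response, two-sided 5%, 4,000 trials per setting. The between-group test is taken as a two-sample t-test on change, since the arms are independent.

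| k | log-SD of response | t on change | raw ANCOVA | log(1 + count) ANCOVA | share of gain from baseline adjustment |
|---|---|---|---|---|---|
| 1 | 0.5 | 22.9% | 55.9% | 56.5% | 33.0 / 33.6 = 98% |
| 0.5 | 0.7 | 13.5% | 31.5% | 38.8% | 18.0 / 25.3 = 71% |
| 1 | 1.0 | 14.3% | 22.6% | 32.0% | 8.3 / 17.7 = 47% |
| 0.5 | 1.0 | 9.6% | 16.1% | 27.6% | 6.5 / 18.0 = 36% |

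The last column is (raw ANCOVA - t) / (log ANCOVA - t). A separate rerun gave 10-22%, 18-55% and 28-57% for the three methods, and 24-52% for rank ANCOVA, with null rejection rates of 4-6%. A Wilcoxon test on change reached only 12-25%. With 30% of women dry at baseline (assumed), the planned test has 7-16% and log ANCOVA 20-41%.

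**4. A second set of assumptions.** Mean 4 to 8 among women who leak, shape 0.8 to 2, 0 to 30% dry, follow-up multipliers 0.5 against 0.25. Power was 11-23% for the t-test, 27-60% for raw ANCOVA and 30-60% for log ANCOVA. Across this set's leak scenarios, the three most extreme of 23 women carried 56-72% of the within-arm sum of squares of change, against about 50% for near-symmetric daily voids. Type I error of the t-test was 4-6% in every null scenario.

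**5. Nighttime and daily voids.** These inputs are also assumed.

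- Nighttime voids (mean 4 per 48 hours, bilateral-to-unilateral ratio 0.7): about 16-19% for the planned test and 22-33% with baseline adjustment. A separate run (25% fall, shape 3 to 5, log-SD 0.3 to 0.5) gave 21-30% for raw ANCOVA and 21-29% for log. In the second set of assumptions, skewness of change was only -0.1 to -0.5 and the top-three share 52-53%, so there is no heavy tail.
- Daily voids (mean 20 per 48 hours, ratio 0.85): about 22-24% for the planned test and 29% adjusted. A separate run gave 29-30% for raw ANCOVA and 26-29% for log.

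**The case against.** The strongest reply is that nothing here is invalid. The t-test holds its error rate, these are secondary outcomes, and the plan claims power only for the OAB-q. That stands: the point is about efficiency and interpretation.

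A reader might infer three stronger things that the documents and figures do not support.

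- **That the raw scale is the flaw for all the diary counts.** Baseline adjustment alone gives 36-98% of the gain for leaks. For nighttime and daily voids the log scale adds nothing.
- **That heavy leakers do set the variance.** The documents contain no leak data. The mechanism is plausible because leakage is not an entry requirement, but its strength rests on the assumed shape and share of dry women.
- **That carrying the baseline Wilcoxon test over to the outcomes would cure this.** A rank test on unadjusted change gains almost nothing.

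Two further objections also stand. First, sample size is a large part of the shortfall: no method reaches 80% in these scenarios, and at 1% log ANCOVA for leaks has only 10-31%. Second, a log analysis changes the quantity estimated. The protocol defines the outcome as a change in number of episodes, whereas a ratio of (1 + count) depends on the added constant and the time unit. For a fall from 6 to 3 per 48 hours the ratio is 4 / 7 = 0.57. Expressed per 24 hours (3 to 1.5) it is 2.5 / 4 = 0.63.

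**Conclusion.** The concern holds as one of lost efficiency. Not adjusting for baseline costs power for all three diary counts: substantially for leaks in most settings, moderately for nighttime voids and little for daily voids. For leaks, a log or rank scale adds materially to baseline adjustment only where skew or variation in response is large.

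The plan's text is certain; the power figures are conditional on distributions that the documents do not supply. Two differing sets of assumptions agree that the planned leak test is weak and that baseline adjustment improves it. A null leak result under the current plan would say little, and under the improved analysis it would often still be inconclusive. This is a worthwhile, inexpensive improvement to secondary analyses. It does not threaten the primary result.

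**What to change.** In Statistical Analysis:

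1. For daily voids and nighttime voids, replace the between-group t-test on change with ANCOVA of the final count on arm and baseline count. The arm effect remains a difference in counts, so the protocol's outcome definition is kept.
2. For incontinence episodes, use ANCOVA of log(1 + final 48-hour count) on arm and log(1 + baseline 48-hour count), or rank ANCOVA. With the log model, report the back-transformed ratio with its 95% interval. Show raw means and medians by arm beside it.
3. Do not substitute quasi-Poisson regression without a small-sample variance correction. Its simulated Type I error for leaks was 6-13%.
4. State that the diary comparisons are not powered, and how many tests the Bonferroni adjustment covers, since it lowers power further. Say also that the between-group test in the current wording is two-sample, not paired.

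The change needs no new data and no extra participants. Its cost is that the log-scale leak effect is a ratio of (1 + count), tied to the added constant and the 48-hour unit, and is harder to read than a difference in episodes.
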